### 1. SYNOPSIS

Name of Sponsor/Company: SANTEN SAS, France

Name of Active Ingredient: Ciclosporin

**Title of Study:** A Phase IIIb, prospective, interventional, multicentre, three-year study to explore the long-term evolution of sign and symptoms, and occurrence of complications in Dry Eye Disease patients with severe keratitis receiving IKERVIS® (1mg/ml ciclosporin) eye drops

### **Coordinating Investigators:**

Studied	period	(vears):
Studied	periou	( ) COLL D).

Estimated date first patient enrolled: February 2019

Estimated date last patient completed: February 2023

**Phase of development:** 

IIIb

Objectives:

### **Primary:**

- To evaluate the long-term efficacy of a continuous treatment of IKERVIS® (1mg/mL ciclosporin) eye drops in adult dry eye disease (DED) patients with severe keratitis on corneal sign and DED symptoms, and to estimate the lag time (if any) to improvement in symptoms (if any).
- To assess the ocular surface complications (defined as corneal ulceration, corneal perforation, loss of visual acuity, and ocular infection) over the three-year study period.

### Secondary:

- To evaluate the efficacy parameters (signs and symptoms), the ocular surface complications, and the quality of life over treatment Periods 1 and 2.
- For 12-month markedly improved patients, to evaluate and compare signs and symptoms evolution in IKERVIS® group versus Vehicle group during the randomised period of the study (Period 2).
- To evaluate the safety and tolerability of IKERVIS® (1mg/mL ciclosporin) eye drops treatment over the three-year study period.

### **Methodology:**

Phase IIIb, prospective, interventional, multicentre study.

Duration of the study:

All enrolled patients will enter a period of 12 months of treatment (Period 1) and attend 5

### visits:

- Period 1 (12-month open-label IKERVIS® treatment period): Baseline visit (Day 1), Month 3, Month 6, Month 9 and Month 12
- At Month 12 visit, markedly improved patients will continue the study during 24 additional months until Month 36 (Period 2) and will be randomised to receive IKERVIS® or vehicle (using a ratio of 3:2) in a double-masked fashion; the patients will attend 8 visits: Period 2 (Double-masked randomised period IKERVIS® or vehicle treatment for markedly improved partients at Month 12): Month 15, Month 18, Month 21, Month 24, Month 27, Month 30, and Month 33 visits and Final visit Month 36

Markedly improved patients are defined as patients having a corneal fluorescein staining (CFS) score improvement from baseline of 2 grades or more on the modified Oxford scale [unless if the patient had a CFS score of 5 at baseline, the improvement in CFS has to be 3 grades or more] in the analysis eye.

Patients who will not be markedly improved at Month 12 (cf. definition above) will be early terminated from the study.

**Number of patients (planned):** 350 DED adult patients with severe keratitis having CFS grade 3 or above on the modified Oxford scale and with at least half of them having a CFS grade 4 or 5.

It is expected that almost 70% of the included patients (approximately 245 patients) would enter the Period 2 (Double-masked randomised period) after Month 12.

This study will be conducted in about 52 trial sites.

### Diagnosis and main criteria for inclusion:

### Patient eligibility is determined according to the following inclusion criteria:

- 1. In the opinion of the investigator, the patient is capable of understanding and complying with protocol requirements.
- 2. The patient has signed and dated a written informed consent form and any required privacy authorization prior to the initiation of any study procedures.
- 3. Male or female patient is aged 18 years or above.
- 4. At least 4 weeks of use of tear substitutes prior to the Baseline Visit.
- 5. DED patients with severe keratitis defined as the following:
  - CFS score of 3, 4 or 5 on the modified Oxford scale in at least one eye at Baseline Visit

AND

• Schirmer test without anaesthesia scored < 10 mm/5min in the same eye at Baseline Visit.

AND

- At least two moderate to very severe symptoms of dry eye disease with a score ≥2 (severity graded on a 0 to 4 grade scale), among the following symptoms: burning/stinging, foreign body sensation, eye dryness, eye pain and blurred/poor vision at Baseline Visit.
- 6. Patient must be willing and able to undergo and return for scheduled study-related examinations.

## Any patient who meets any of the following criteria will not qualify for entry into the study:

- 1. Active herpes keratitis or history of ocular herpes.
- 2. History of ocular trauma or ocular infection (viral, bacterial, fungal, protozoal) within 90 days before the Baseline Visit.
- 3. Any ocular diseases other than DED requiring topical ocular treatment during the course of the study. Patients taking preservative-free IOP lowering medications are eligible for study enrolment.
- 4. Concurrent ocular allergy (including seasonal conjunctivitis) or chronic conjunctivitis other than dry eye.
- 5. Anticipated use of temporary punctal plugs during the study. Patients with punctal plugs placed prior to the Baseline Visit are eligible for enrolment; however, punctal plugs must remain in place during the study.
- 6. Best corrected distance visual acuity (BCDVA) score  $\leq 20/200$  Snellen in each eye.
- 7. Presence or history of any systemic or ocular disorder, condition or disease that could possibly interfere with the conduct of the required study procedures or the interpretation of study results or judged by the investigator to be incompatible with the study (e.g., diabetes with glycemia out of range, thyroid malfunction, uncontrolled autoimmune disease, current systemic infections, ocular infection...).
- 8. Known hypersensitivity to one of the components of the study or procedural medications (e.g., fluorescein, etc...).
- 9. History of ophthalmic malignancy.
- 10. History of malignancy (other than ophthalmic) in the last 5 years
- 11. Anticipated change during course of the study in the dose of systemic medications that could affect a dry eye condition [mainly, estrogen-progesterone or other estrogen derivatives (only allowed for post-menopausal women), pilocarpine, isotretinoine, tetracycline, antihistamines, tricyclic antidepressants, anxiolytics, antimuscarinics, beta-blocking agents, phenothiazines, omega-3, systemic corticosteroids]. These treatments are allowed during the study provided they remain stable throughout the course of the study.
- 12. Use of topical ciclosporin in the past 3 months prior to Baseline visit.

6

- 13. Any change in systemic immunosuppressant drugs within 30 days before the Baseline Visit or anticipated change during the course of the study.
- 14. Pregnancy or lactation at the Baseline Visit.
- 15. Women of childbearing potential not using a medically acceptable, highly effective method of birth control (such as hormonal implants, injectable or oral contraceptives together with condoms, some intrauterine devices, sexual abstinence or vasectomised partner) from the Baseline Visit throughout the conduct of the study treatment periods and up to 2 weeks after the study end. Post-menopausal women (two years without menstruation) do not need to use any method of birth control.
- 16. Participation in a clinical trial with an investigational substance within the past 30 days prior to Baseline Visit.
- 17. Participation in another clinical study at the same time as the present study.

### Investigational product, dosage and mode of administration:

Investigational product: IKERVIS® (1 mg/ml ciclosporin) eye drops single-dose containers.

Investigational product dose: 1mg/ml ciclosporin (CsA)

Regimen: Instillation of one drop in each affected eye, once daily at bedtime.

### **Duration of treatment:**

The duration of treatment is up to 36 months except for non markedly improved patients at Month 12 for whom the duration of treatment is up to 12 months.

### Reference therapy, dosage and mode of administration:

Reference Product (for markedly improved patients at Month 12 to use in Period 2): Vehicle of IKERVIS® - sterile, ophthalmic cationic oil-in-water emulsion containing no active substance.

Regimen: Instillation of one drop in each affected eye, once daily at bedtime.

### **Criteria for evaluation:**

### **Efficacy:**

Efficacy will be assessed by evaluating CFS score, symptoms score ("Symptom Assessment iN Dry Eye" [SANDE] questionnaire and 5-point scale), correlation between sign and symptoms, conjunctival fluorescein staining score, TBUT, Schimer test, use of artificial tears, and quality of life.

### Safety:

Safety assessments will be composed of ocular surface complications, adverse events, Intraocular Pressure (IOP), and Best Corrected Distance Visaul Acuity (BCDVA)

### **Endpoints:**

### **Primary Efficacy and Safety Endpoints:**

- The correlation between mean change from baseline in CFS score and SANDE symptoms score at each visit, and cross correlation of sign at visit X versus symptoms at visit X+i (i starting from 0), if any.
- Incident rate and time to onset of ocular surface complications (defined as corneal ulceration, corneal perforation, loss of visual acuity and ocular infection)

### **Secondary Endpoints:**

### **Efficacy:**

### A) In Period 1:

- CFS score and change from baseline at each visit
- Conjunctival fluorescein staining score and change from baseline at each visit
- SANDE symptoms score and change from baseline at each visit
- Symptoms score (5-point scale) and change from baseline at each visit, for each of the five symptoms assessed
- Occurrence and time to become markedly improved (defined as CFS score improvement of 2 or more on the modified Oxford scale at Month 12)
- TBUT and change from baseline at each visit
- Schirmer test and change from baseline at Month 12 visit
- Use of Artificial Tears over the last week and change from baseline at each visit

### B) In Period 2:

- CFS score and change from Month 12 visit at each visit
- Conjunctival fluorescein staining score and change from Month 12 at each visit
- SANDE symptoms score and change from Month 12 visit at each visit
- Symptoms score (5-point scale) and change from Month 12 visit at each visit, for each of the five symptoms assessed
- TBUT and change from Month 12 visit at each visit
- Schirmer test and change from Month 12 visit at Month 24 and Month 36 visits
- Use of Artificial Tears (over the last week and change from Month 12 visit at each visit
- Occurrence and time to relapse (increase of CFS score of 2 or more on the modified Oxford scale)

### C) In entire study:

- CFS score and change from baseline at each visit
- Conjunctival fluorescein staining score and change from baseline at each visit
- SANDE symptoms score and change from baseline at each visit
- Symptoms score (5-point scale) and change from baseline at each visit, for each of the five symptoms assessed
- TBUT and change from baseline at each visit
- Schirmer test and change from baseline at each visit

• Use of Artificial Tears over the last week and change from baseline at each visit

### **Quality of life:**

In the randomised markedly improved population,

• Dry Eye related Quality of life Score (DEQS) overall score, and change from baseline at Month 6, Month 12, Month 18, Month 24, Month 30 and Month 36 Visits. Change from Month 12 will also be summarized for scores collected in Period 2.

### Safety and Tolerability:

In the Safety population, safety and tolerability endpoints are:

- Intraocular pressure (IOP) and change from baseline at Month 12, Month 24 and Month 36 visits
- Best Corrected Distance Visual Acuity (BCDVA) and change from baseline at Month 6, Month 12, Month 24 and Month 36 visits visits.
- Incidence and severity of ocular and systemic adverse events (AEs) over the three-year study period.

### **Statistical methods:**

### Analysis Eye

All the efficacy analysis will be performed on the analysis eye only that fulfils all the criteria listed under the inclusion criteria #5. If both eyes are eligible, the eye with the highest baseline CFS score will be chosen. If not discriminant, the eye with the lowest Schirmer test value will be chosen. If not discriminant, the right eye will be chosen as the analysis eye.

### Analysis Populations

Analysis populations are defined based on study period.

### For Period 1:

- The **Full Analysis Set (FAS)** population consists of all enrolled subjects who received at least one dose of the study medication and had at least one post-baseline sign or symptom assessment of the study eye during Period 1. This will be the population used for efficacy analyses.
- The Per-Protocol Set (PPS) will be a subset of FAS, restricted to the subjects who fulfill the protocol in the terms of the eligibility, interventions, and outcome assessment. It will be the analysis population for some sensitivity analyses.
- The **Safety population** consists of all patients enrolled in Period 1 who received at least one dose of the study medication and for whom any follow-up information is available. It will be the analysis population for safety analyses to be performed with subjects as treated.
- The following analysis subpopulation will be defined according to the treatment response to efficacy variables:

Markedly Improved Patients are defined as FAS subjects who achieve CFS score improvement from baseline of 2 grades or more (unless if the patient had a CFS score of 5 at baseline, the improvement in CFS has to be 3 grades or more) at Month 12 visit.

### For Period 2:

- The **FAS** population consists of all randomised patients who received at least one dose of the study medication and had at least one post-Month 12 sign or symptom assessment of the study eye during Period 2. This will be the population used for efficacy analyses.
- The Per-Protocol Set (PPS) will be a subset of FAS, restricted to the subjects who fulfill the protocol in the terms of the eligibility, interventions, and outcome assessment. It will be the analysis population for some sensitivity analyses.
- The **Safety population** consists of all patients enrolled in Period 2 for whom any follow-up information is available. It will be the analysis population for safety analyses to be performed with subjects as treated.

### For entire study:

- The FAS population consists of the Markedly Improved Patients who were randomised to IKERVIS in Period 2 and received at least one dose of IKERVIS in Period 2 and had at least one post-Month 12 sign or symptom assessment of the study eye during Period 2.
- The Per-Protocol Set (PPS) will be a subset of FAS, restricted to the subjects who fulfill the protocol in the terms of the eligibility, interventions, and outcome assessment. It will be the analysis population for some sensitivity analyses.
- The **Safety population** consists of the Markedly Improved Patients who were randomised to IKERVIS in Period 2 and had at least one post-Month 12 sign or symptom assessment of the study eye during Period 2. It will be the analysis population for safety analyses to be performed with subjects as treated.

The Sjögren patients population will be specifically described separately for some analyses.

### Analysis of Demographics and Baseline Characteristics

Descriptive summaries will be performed for demographic (including age, gender, race, ethnicity, female patients' menopausal status) and baseline characteristics variables (including Sjögren Disease status, time since diagnosis, past surgery or laser treatment in the analysis eye, and smoking status).

In addition, medical history (ocular and systemic) and prior and concomitant medication use will be summarised by treatment response status and for the overall population.

### Analysis of Primary Efficacy and Safety Endpoints

Spearman correlation coefficient will be obtained between mean change from baseline in CFS score at visit X and SANDE symptoms score at each visit X+i for each FAS population in Period 1, Period 2, and entire study. For Period 1, visit X includes Day1, Month 3, Month 6, Month 9 and Month 12, and i is from 0 (Day 1) up to 4 (Month 12). For Period 2, X includes Month 12, Month 15, Month 18, Month 21, Month 24, Month 27, Month 30, Month 33, and Month 36, and i is from 0 (Month 12) up to 8 (Month 36). Correlation coefficient will be analized by treatment group. For entire study, visit X includes all the scheduled visits from Day 1 to Month 36, and i is from 0 (Day1) up to 12 (Month 36). Missing data will not be imputed.

The incident rate of ocular surface complications (defined as corneal ulceration, corneal perforation, loss of visual acuity, and ocular infection) will be estimated with its 95% CI for each safety population in Period 1, Period 2, and the entire study. The analysis for safety population in Period 2 will be conducted by treatment group. These rates will be compared to existing epidemiologic rates in a comparable population. Time to onset and time to resolution of the ocular complications will also be summarized.

Missing data will not be imputed.

### Analysis of Secondary Efficacy Endpoints

For FAS population in Period 1, Period 2 and entire study, mean scores of CFS, conjunctival fluorescein staining, symptoms (SANDE and 5-point scale), TBUT, Schirmer test, artificial tear use and quality of life overall DEQS scores, and their change from baseline (Period 1 and Period 2) or from Month 12 (Period 2) will be summarized by analysis visit. The analysis for FAS population in Period 2 wil be performed by planned treatment groups.

Occurrence and time to relapse defined as an increase of CFS modified Oxford score of 2 or more will be summarized for FAS population in Period 2 by treatment group.

Survival analysis method will be employed to analyze the time to become Markedly Improved Patients for Period 1.

Summary statistics on the scores of Quality of Life variables and exploratory investigation variables will be provided as well as their change from baseline at each visit.

Missing data will not be imputed.

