# 7.4. Subject Discontinuation or Withdrawal Criteria

The primary reason for discontinuation or withdrawal of the patient from the study should be recorded in the electronic case report form (eCRF) using the following categories.

- 1. Adverse event (AE). The patient has experienced an /AE that requires early termination because continued participation imposes an unacceptable risk to the patient's health or the patient is unwilling to continue because of an AE. Patients discontinued for drug-related AE(s) will be followed-up after patient's discontinuation until the event is resolved, stabilized or a final assessment can otherwise be done by the investigator.
- 2. Protocol deviation. The discovery after administration of the first dose of study drug that the patient failed to meet protocol entry criteria or did not adhere to protocol requirements, and continued participation poses an unacceptable risk to the patient's health.
- 3. Lost to follow-up. The patient did not return to the clinic and attempts to contact the patient were unsuccessful. In case of a patient lost-to-follow-up, the investigator must do his/her best to contact the patient initially by phone, then by letter, and finally by certified mail. If no response is obtained from the patient, the investigator is encouraged to contact one of the patient's relatives or his/her general physician. These attempts must be documented and associated documentation filed in the patient medical chart.
- 4. Voluntary withdrawal. The patient (or patient's legally acceptable representative) wishes to withdraw from the study. The reason for withdrawal, if provided, should be recorded in the eCRF.
  - Note: All attempts should be made to determine the underlying reason for the withdrawal and, where possible, the primary underlying reason should be recorded (i.e., withdrawal due to an AE should not be recorded in the "voluntary withdrawal" category).
- 5. Study termination. The Sponsor, IRB, IEC, or regulatory agency terminates the study.
- 6. Lack of efficacy. the patient or the physician does not feel that the study medication has adequately relieved his/her symptoms.
- 7. Pregnancy. The patient is found to be pregnant.
  - Note: If the patient is found to be pregnant, the patient must be withdrawn immediately. The procedure is described in Section 12.2.1.5.
- 8. Investigator decision due to non-compliance (to IMP, study visits or study related procedure).
- 9. Other reason, specify.

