# 13.8. Handling of Missing Values

No imputation for missing data will be performed on primary and secondary endpoint analyses. Unless specified otherwise, descriptive summaries will be based on observed cases.

For medical events including AEs, completely or partially missing onset and resolution dates will be imputed in a conservative fashion to be detailed in the Statistical Analysis Plan (SAP). Same rules will be followed to impute the completely or partially missing start and end dates of non-study medications.

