5. GENERAL CONSIDERATIONS

All measures will be summarized for Overall subjects in Period 1 and by treatment group in Period 2 as well as for the entire study descriptively. Continuous variables will be summarized using descriptive statistics such as number of observations (n), mean, standard deviation, median, minimum, and maximum. Categorical variables will be tabulated using frequency (n) and percent (%).

Unless otherwise specified, the following conventions on decimal places will be followed in reporting numerical results.

Statistic	Reporting Decimal Places
Range (Low Value, High Value)	Recorded decimal places
Mean, Median	Recorded value + 1 decimal places
Confidence interval, standard deviation, standard error	Recorded value + 2 decimal places
P-value	4 Decimal places (ex. 0.0021)

No statistical testing will be conducted for both the efficacy and safety measures for Period 1 in this study.

All data summary/analysis will be performed using SAS Version 9.4 or later. Individual data, including relevant derived variables, will be listed. Additional analyses not specified in this SAP may be conducted if deemed necessary and will be documented in the CSR.

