5.2. Handling of Missing Data

No imputation for missing data will be performed on any efficacy and safety endpoints. Unless specified otherwise, descriptive summaries will be based on observed cases.

Completely or partially missing onset and resolution dates for AEs, Concomitant Medications (CM), and Medical History (MH) will be imputed in a conservative fashion as follows:

Incomplete Adverse Event Onset Date

- 1. Year imputation
 - o If *year* is missing (or AE onset date is completely missing), then the onset date will not be imputed.
- 2. Month imputation
 - o If *year* is not missing but *month* is missing, then:

- If *year* = year of first study dose date, then set the *month* and *day* to the day and month of first study dose
- Else if $year \neq year$ of first study dose: set *month* to January

3. Day imputation

- o If day is missing (month and year not missing), then:
 - If year = year and month = month of first study dose, then set day to day of first study dose
 - Else if $year \neq year$ and $month \neq month$ of first study dose, then set day to first day of the month in the year

Incomplete Adverse Event Resolution Date

Do not impute if any resolution date is missing.

If the duration of AE is needed, the following approach may be considered:

- o If year is missing (or AE resolution date is completely missing): do not impute
- o If *year* is not missing but *month* and *day* are missing: impute December 31st for missing *month* and *day*
- o If *year* and *day* are not missing but *month* is missing: impute December for missing *month*
- o If *year* and *month* are not missing but *day* is missing: impute last day of the *month* for missing *day*.

Incomplete CM or MH Onset Date

- 1. If year is missing (or CM/MH onset date is completely missing), do not impute
- 2. If *year* is not missing but *month* and *day* are missing, impute January 1st for missing *month* and *day*
- 3. If year and day are not missing but month is missing, impute January for missing month
- 4. If year and month are not missing but day is missing, impute 01 for missing day

Incomplete CM or MH Resolution Date

- 1. If a resolution date is completely missing, do not impute.
- 2. If year is not missing but month and day are missing, use the last day of the year to impute the missing month and date parts of the resolution date.

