In each endpoint, separate MMRM will be applied, and the analysis will be performed using observed case of each endpoint with the FAS population Period 2. Each model will include (randomized) treatment, visit, treatment by visit interaction as fixed effects, and the corresponding Month 12 value and geographic region (Europe vs. non-Europe) as covariates. Within-subject errors will be modeled using an unstructured (UN) covariance matrix. If there are convergence issues, covariance matrix structures other than unstructured will be tried in the following order: (1) heterogeneous Toeplitz (TOEPH), (2) heterogeneous autoregressive of order 1 (ARH(1)), (3) heterogeneous compound symmetry (CSH), and (4) compound symmetry (CS). The first covariance structure that converges will be used.

Least squares mean values for each treatment arm and the differences between least squares treatment arm means and associated 95% confidence intervals with t-distribution will be reported for each visit in addition nominal p-value.

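### Period 1 changes in signs and symptoms are reported on observed cases only, so the Month 12 mean is likely to be too favourable if patients who leave early do worse

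*Protocol*

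**What the plan says.** The protocol synopsis (Analysis of Secondary Efficacy Endpoints) plans by-visit means and changes: "For FAS population in Period 1, Period 2 and entire study, mean scores of CFS, conjunctival fluorescein staining", followed by the symptom scores and other measures. It adds that "Missing data will not be imputed". Protocol 13.8 repeats the rule: "No imputation for missing data will be performed on primary and secondary endpoint analyses". SAP 5.2 widens it: "No imputation for missing data will be performed on any efficacy and safety endpoints", and "Unless specified otherwise, descriptive summaries will be based on observed cases". SAP 5 adds "No statistical testing will be conducted for both the efficacy and safety measures for Period 1 in this study".

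SAP 8.2.1 lists n, mean, SD, median, minimum and maximum for each continuous endpoint, with shift tables for the staining scores. Its MMRM estimates change from Month 12 only: "the analysis will be performed using observed case of each endpoint with the FAS population Period 2". The sensitivity analysis in SAP 8.1.2 covers the primary efficacy endpoint, in the per-protocol sets.

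Under SAP 6, one post-baseline assessment is enough for FAS Period 1. Under SAP 4.1.4, the Month 12 window opens at Day 316. Protocol 7.4 lists adverse event and lack of efficacy among the withdrawal categories, the latter meaning that "the patient or the physician does not feel that the study medication has adequately relieved his/her symptoms". Protocol 7.5 does not replace leavers, but asks for the end-of-study assessments at exit.

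**The concern.** The first primary objective is long-term efficacy on the corneal sign and on symptoms. The primary efficacy endpoint is a correlation, which does not measure how much patients improve. The size of improvement in the first year is therefore read from these secondary means, first at the interim analysis. Period 1 is also the only stage in which every enrolled patient is followed on IKERVIS.

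The Month 12 mean carries the label FAS Period 1 but is computed only in patients with a Month 12 value. If those who leave early had improved less, the mean describes the patients who stayed and looks better than the set it is named after. Nothing planned for the score changes would show this. The Period 1 disposition table in SAP 7.1 separates completers from non-completers, and names discontinuation reasons only for Period 2.

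**Working it through.** **1. Who is missing at Month 12.** Take a patient who leaves at Day 120 with an early-termination visit. Day 120 lies in the Month 3 window (Days 2 to 135). If the Month 3 visit took place at Day 90, it is closer to target and is the value kept. The exit value then appears at no visit, and the patient is absent from Months 6, 9 and 12 while remaining in FAS Period 1. An exit from Day 316 on, if assessed, does count at Month 12. So do patients not markedly improved at Month 12, who are withdrawn at that visit after assessment (protocol 10.1.3).

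**2. The plan's own figures.** The documents state no figure for the Period 1 mean change. The only CFS standard deviation they give is 1.10, in the Period 2 sample-size statement (protocol 13.1.1). That statement reproduces at an assumed two-sided 5% level: 0.4 / (1.10 × √(1/147 + 1/98)) = 0.4 / 0.1434 = 2.79, and Φ(2.79 − 1.96) ≈ 0.796, against the stated 80%. Nothing below depends on it; it only supplies a scale.

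**3. Direct arithmetic.** Let d be the share with no Month 12 value, and m_S and m_L the mean changes of stayers and leavers. The all-patient mean is (1 − d)·m_S + d·m_L, so the observed-case mean overstates improvement by d × (m_L − m_S). For illustration, set m_S = −1.764 and m_L = −1.418, the Month 6 active and vehicle changes of the pivotal trial (protocol 4.1.1). The difference is 0.346.

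- d = 10%: 0.10 × 0.346 = 0.035 grade
- d = 20%: 0.20 × 0.346 = 0.069 grade
- d = 30%: 0.30 × 0.346 = 0.104 grade
- m_L = m_S: zero at any d
- m_L = 0 (leavers unchanged from baseline): 0.176, 0.353 and 0.529 grade, an extreme assumption

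**4. Simulation.** Assumptions: 350 patients; Months 3, 6, 9 and 12; true Month 12 mean −1.764; odds of leaving multiplied by 2.7 (log-odds +1) per grade less improvement, except where exit is random. Drop-out rates, earlier visit means and correlations are all assumed.

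| Exit depends on | SD and correlation | Drop-out | Observed-case overstatement | Left after a likelihood model |
|---|---|---|---|---|
| last observed CFS | 1.2; constant 0.6 | 13.2 / 20.9 / 27.4% | 0.10 / 0.17 / 0.21 | about 0 |
| last observed CFS | 1.10; 0.6 decaying with lag | 10 / 20 / 30% | 0.04 / 0.09 / 0.13 | about 0 |
| unseen CFS | 1.10; 0.6 decaying with lag | 10 / 20 / 30% | 0.08 / 0.15 / 0.22 | 0.05 / 0.10 / 0.15 |
| nothing (random) | 1.10; 0.6 decaying with lag | 10 / 20 / 30% | about 0 | about 0 |

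First row: observed-case means −1.867, −1.931 and −1.974 less the true −1.764; the model returned −1.762, −1.766 and −1.759. Third row at 10%: the model removes (0.079 − 0.054) / 0.079 = 32% of the bias, about one third.

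**5. Exit driven by symptoms.** The lack-of-efficacy criterion is about symptoms, and protocol 4.2 says these usually correlate poorly with staining. With the first row's settings, but exit depending on a symptom variable correlated 0.3 with CFS, the CFS overstatement is about 0.03 to 0.06 grade at 13% to 27% drop-out. At a correlation of 0.1 and 13% drop-out it is about 0.01. The symptom means themselves would then carry the stronger selection; that was not quantified.

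**The case against.** The strongest reply is that Period 1 is single-arm, untested and descriptive, and that the bias is hypothetical. A reader might infer that the open-label improvement is overstated as a matter of fact. The documents do not support that: they give neither the drop-out rate nor the outcomes of leavers, and the bias is zero if the two groups do equally well.

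Intolerance is weak evidence of a worse score. Instillation-site pain reached 29.2% on IKERVIS in the pivotal trial, but it was mostly mild, no discontinuation rate is given, and pain need not mean worse staining. Nor should the bias be set against the between-arm differences of 0.35 and 0.23 grade in the two earlier trials. This is a single-arm change from baseline, and vehicle alone moved by −1.418 in the pivotal trial.

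The plan is also not bare. CFS shift tables are planned, marked improvement in Period 1 gets occurrence rates and Kaplan-Meier analysis, and n at each visit shows attrition. Non-responders seen at Month 12 are counted. From n and SD a reader can build an approximate interval, though only for those who stayed.

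All of this stands, and it lowers the severity. It does not remove the point that a descriptive mean can be biased and that nothing planned for the score changes examines it. An estimate with an interval is not a test, so the rule against testing in Period 1 is no obstacle.

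**Conclusion.** The point holds as a minor one. Period 1 score changes are observed-case summaries without a confidence interval or missing-data analysis, and patients who leave before Day 316 are missing from a Month 12 mean labelled with the set they belong to. The mean is likely to be too favourable if leavers do worse, and unbiased otherwise. For CFS, roughly 0.03 to 0.2 grade is plausible at an assumed 10% to 30% drop-out; the figure depends on the SD, the within-patient correlation and whether exit follows staining or symptoms. The larger values in step 3 need every leaver to show no improvement at all, which nothing in the documents suggests.

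A reader might extend the same argument to the three-year changes from baseline. It carries over only in part. In SAP 6, FAS Entire Study is restricted to randomised patients, that is, Month 12 responders, so Period 1 leavers are excluded by definition. A model there would address Period 2 drop-out, not the selection on response.

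**What to change.** - In SAP 8.2.1, beside the observed-case table, add an MMRM of change from baseline at Months 3 to 12 in FAS Period 1, with visit as fixed effect, baseline value and region as covariates, and unstructured covariance with the SAP's existing fallback order. Report the least-squares mean and 95% interval per visit, with no test. This suits the endpoints measured at every visit; Schirmer has only one post-baseline value in Period 1 and gains nothing.
- State how early-termination values that lose out in the visit window enter the analysis.
- In SAP 7.1, tabulate missing Month 12 data by withdrawal reason; protocol 7.4 already has the reasons recorded.
- Because an MMRM corrects only drop-out explained by observed scores, add one sensitivity analysis assuming worse outcomes after exit for lack of efficacy or an adverse event. If it uses imputation, SAP 5.2 needs an exception, recorded in SAP 10.
- For the three-year changes from baseline, state the restriction to randomised Month 12 responders as a limit on interpretation.

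The cost is SAP text, adapted code and some extra output, with no new data. The downside is that the MMRM relies on a missing-at-random assumption, which the sensitivity analysis is there to probe.
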